7.1.6.3 Post-Treatment Visits

The mandatory Safety Follow-Up Visit should be conducted approximately 30 days after the last dose of trial treatment or before the initiation of a new anti-cancer treatment, whichever comes first. All AEs that occur prior to the Safety Follow-Up Visit should be recorded. Subjects with an AE of Grade > 1 will be followed until the resolution of the AE to Grade 0-1 or until the beginning of a new anti-neoplastic therapy, whichever occurs first. SAEs that occur within 90 days of the end of treatment or before initiation of a new anti-cancer treatment should also be followed and recorded.

7.1.6.4 Follow-up Visits

Subjects who discontinue trial treatment for a reason other than disease progression will move into the Follow-Up Phase and should be assessed every 12 weeks (84 ± 7 days) by radiologic imaging to monitor disease status. Every effort should be made to collect information regarding disease status until the start of new anti-neoplastic therapy, disease progression, death, end of the study or if the subject begins retreatment with pembrolizumab as detailed in Section 7.1.6.2.2. Information regarding post-study anti-neoplastic treatment will be collected if new treatment is initiated.

Subjects who are eligible to receive retreatment with pembrolizumab will move from the follow-up phase to the Second Course Phase when they experience disease progression. Details are provided in Section 6.0 – Trial Flow Chart.

7.1.6.4.1 Survival Follow-up

Once a subject experiences confirmed disease progression or starts a new anti-cancer therapy, the subject moves into the survival follow-up phase and should be contacted by telephone every 12 weeks to assess for survival status until death, withdrawal of consent, or the end of the study, whichever occurs first.

7.2 Assessing and Recording Adverse Events

An adverse event is defined as any untoward medical occurrence in a patient or clinical investigation subject administered a pharmaceutical product and which does not necessarily have to have a causal relationship with this treatment. An adverse event can therefore be any unfavorable and unintended sign (including an abnormal laboratory finding, for example), symptom, or disease temporally associated with the use of a medicinal product or protocol-specified procedure, whether or not considered related to the medicinal product or protocol-specified procedure. Any worsening (i.e., any clinically significant adverse change in frequency and/or intensity) of a preexisting condition that is temporally associated with the use of the Merck's product, is also an adverse event.

Changes resulting from normal growth and development that do not vary significantly in frequency or severity from expected levels are not to be considered adverse events. Examples of this may include, but are not limited to, teething, typical crying in infants and children and onset of menses or menopause occurring at a physiologically appropriate time.

Merck product includes any pharmaceutical product, biological product, device, diagnostic agent or protocol-specified procedure, whether investigational (including placebo or active comparator medication) or marketed, manufactured by, licensed by, provided by or distributed by Merck for human use.

Adverse events may occur during the course of the use of Merck product in clinical trials or within the follow-up period specified by the protocol, or prescribed in clinical practice, from overdose (whether accidental or intentional), from abuse and from withdrawal.

Adverse events may also occur in screened subjects during any pre-allocation baseline period as a result of a protocol-specified intervention, including washout or discontinuation of usual therapy, diet, placebo treatment or a procedure.

All adverse events will be recorded from the time the consent form is signed through 30 days following cessation of treatment and at each examination on the Adverse Event case report forms/worksheets. The reporting timeframe for adverse events meeting any serious criteria is described in section 7.2.3.1.

Adverse events will not be collected for subjects during the pre-screening period (for determination of archival tissue status) as long as that subject has not undergone any protocol-specified procedure or intervention. If the subject requires a blood draw, fresh tumor biopsy etc., the subject is first required to provide consent to the main study and AEs will be captured according to guidelines for standard AE reporting.

7.2.1 Definition of an Overdose for This Protocol and Reporting of Overdose to the Sponsor and to Merck

For purposes of this trial, an overdose will be defined as any dose exceeding the prescribed dose for pembrolizumab by 20% over the prescribed dose. No specific information is available on the treatment of overdose of pembrolizumab. In the event of overdose,

Protocol date: August 30, 2016

Confidential

pembrolizumab should be discontinued and the subject should be observed closely for signs of toxicity. Appropriate supportive treatment should be provided if clinically indicated.

[figure not shown]
If an adverse event(s) is associated with (“results from”) the overdose of a Merck product, the adverse event(s) is reported as a serious adverse event, even if no other seriousness criteria are met.

If a dose of Merck’s product meeting the protocol definition of overdose is taken without any associated clinical symptoms or abnormal laboratory results, the overdose is reported as a non-serious Event of Clinical Interest (ECI), using the terminology “accidental or intentional overdose without adverse effect.”

7.2.2 Reporting of Pregnancy and Lactation to the Sponsor and to Merck

Although pregnancy and lactation are not considered adverse events, it is the responsibility of investigators or their designees to report any pregnancy or lactation in a subject (spontaneously reported to them), including the pregnancy of a male subject's female partner that occurs during the trial or within 120 days of completing the trial. All subjects and female partners of male subjects who become pregnant must be followed to the completion/termination of the pregnancy. Pregnancy outcomes of spontaneous abortion, missed abortion, benign hydatidiform mole, blighted ovum, fetal death, intrauterine death, miscarriage and stillbirth must be reported as serious events (Important Medical Events). If the pregnancy continues to term, the outcome (health of infant) must also be reported.

7.2.3 Immediate Reporting of Adverse Events to the Sponsor and to Merck

7.2.3.1 Serious Adverse Events

A serious adverse event is any adverse event occurring at any dose or during any use of Merck’s product that:

- Results in death;
- Is life threatening;
- Results in persistent or significant disability/incapacity;
- Results in or prolongs an existing inpatient hospitalization;
- Is a congenital anomaly/birth defect;
- Is a new cancer (that is not a condition of the study);
- Is associated with an overdose;
- Is another important medical event

Progression of the cancer under study is not considered an adverse event unless it results in hospitalization or death.

Any serious adverse event, or follow up to a serious adverse event, including death due to any cause other than progression of the cancer under study that occurs to any subject from the time the consent is signed through 90 days following cessation of treatment, or the initiation of new anti-cancer therapy, whichever is earlier, whether or not related to Merck product, must be reported within 24 hours to the Sponsor and within 2 working days to [REDACTED]

Non-serious Events of Clinical Interest will be forwarded [REDACTED] handled in the same manner as SAEs.

Additionally, any serious adverse event, considered by an investigator who is a qualified physician to be related to Merck product that is brought to the attention of the investigator at any time outside of the time period specified in the previous paragraph also must be reported immediately to the Sponsor and to Merck.

A copy of all 15 Day Reports and Annual Progress Reports is submitted as required by FDA, European Union (EU), Pharmaceutical and Medical Devices agency (PMDA) or other local regulators. Investigators will cross reference this submission according to local regulations to the [REDACTED] the time of submission.

All subjects with serious adverse events must be followed up for outcome.

7.2.3.2 Events of Clinical Interest

Selected non-serious and serious adverse events are also known as Events of Clinical Interest (ECI) and must be recorded as such on the Adverse Event case report forms/worksheets and reported within 24 hours to the Sponsor and within 2 working days to [REDACTED]

Events of clinical interest for this trial include:

1. an overdose of Merck product, as defined in Section 7.2.1 - Definition of an Overdose for This Protocol and Reporting of Overdose to the Sponsor, that is not associated with clinical symptoms or abnormal laboratory results.
2. an elevated AST or ALT lab value that is greater than or equal to 3X the upper limit of normal and an elevated total bilirubin lab value that is greater than or equal to 2X the upper limit of normal and, at the same time, an alkaline phosphatase lab value that is less than 2X

the upper limit of normal, as determined by way of protocol-specified laboratory testing or unscheduled laboratory testing.*

*Note: These criteria are based upon available regulatory guidance documents. The purpose of the criteria is to specify a threshold of abnormal hepatic tests that may require an additional evaluation for an underlying etiology. The trial site guidance for assessment and follow up of these criteria can be found in the Investigator Trial File Binder (or equivalent).

3. In the event a subject develops any of the following AEs, a detailed narrative of the event should be reported as an ECI to the Sponsor within 24 hours and to [REDACTED] within 2 working days of the event:

- a. Grade \geq 3 diarrhea
- b. Grade \geq 3 colitis
- c. Grade \geq 2 pneumonitis
- d. Grade \geq 3 hypo- or hyperthyroidism

A separate guidance document has been provided entitled “event of Clinical Interest and Immune-Related Adverse Event Guidance Document.” This document provides guidance regarding identification, evaluation and management of ECIs and irAEs. Additional ECIs are identified in this guidance document and also need to be reported to the Sponsor within 24 hours and to [REDACTED] within 2 working days of the event.

Subjects should be assessed for possible ECIs prior to each dose. Lab results should be evaluated and subjects should be asked for signs and symptoms suggestive of an immune-related event. Subjects who develop an ECI thought to be immune-related should have additional testing to rule out other etiologic causes. If lab results or symptoms indicate a possible immune-related ECI, then additional testing should be performed to rule out other etiologic causes. If no other cause is found, then it is assumed to be immune-related.

ECIs that occur in any subject from the date of first dose through 90 days following cessation of treatment, or the initiation of a new anticancer therapy, whichever is earlier, whether or not related to the Merck’s product, must be reported within 24 hours to the Sponsor and to [REDACTED] within 2 working days.

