
Appropriate resuscitation equipment should be available in the room and a physician readily available during the period of drug administration.
 
For Further information, please refer to the Common Terminology Criteria for Adverse Events v4.0 (CTCAE) at http://ctep.cancer.gov
		

5.6.1.1 Supportive Care Guidelines for Events of Clinical Interest and Immune-related Adverse Events (irAEs)

Events of clinical interest of a potential immunologic etiology (irECIs) may be defined as an adverse event of unknown etiology, associated with drug exposure and is consistent with an immune phenomenon. irAEs may be predicted based on the nature of the pembrolizumab compound, its mechanism of action, and reported experience with immunotherapies that have a similar mechanism of action. Special attention should be paid to AEs that may be suggestive of potential irAEs. An irAE can occur shortly after the first dose or several months after the last dose of treatment.

If an irAE is suspected, efforts should be made to rule out neoplastic, infectious, metabolic, toxin or other etiologic causes prior to labeling an adverse event as an irAE.

Recommendations to managing irAEs not detailed elsewhere in the protocol are detailed in Table 6.

Table 6 General Approach to Handling irAEs

irAE	Withhold/Discontinue pembrolizumab?	Supportive Care
Grade 1	No action	Provide symptomatic treatment
Grade 2	May withhold pembrolizumab	Consider systemic corticosteroids in addition to appropriate symptomatic treatment
Grade 3 and Grade 4	Withhold pembrolizumab Discontinue if unable to reduce corticosteroid dose to <	Systemic corticosteroids are indicated in addition to appropriate symptomatic treatment. May utilize 1 to 2 mg/kg prednisone or equivalent per day.

Protocol date: August 30, 2016

Confidential

	10 mg per day prednisone equivalent within 12 weeks of toxicity	Steroid taper should be considered once symptoms improve to Grade 1 or less and tapered over at least 4 weeks.
--	---	--

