6.0 TRIAL FLOW CHART

6.1 Study Flow Chart

Trial Period:	Screening Phase	Treatment Cycles									End of Treatment	Post-Treatment		
							Repeat every 12 weeks					Safety Follow-up ¹⁶	Follow Up Visits ¹⁷	Survival Follow-Up ¹⁸
Treatment Cycle/Title:	Screening Visit	1	2	3	4	5	6	7	8	9				
		0	3	6	9	12	15	18	21	24				
Scheduling Window (Days) ² :	-28 to -1 days		± 3	± 3	± 3	± 3	± 3	± 3	± 3	± 3	At time of Discon	30 days post discon	Every 12 weeks post discon	Every 12 weeks
Administrative Procedures														
Informed Consent ²	X													
Inclusion/Exclusion Criteria	X													
Demographics and Medical History and Prior Medications ³	X													
Concomitant Medication Review	X	X	X	X	X	X	X	X	X	X				
Post-study anticancer therapy status											X	X	X	
Survival Status											X	X	X	
Clinical Procedures/Assessments														
Review Adverse Events ⁴		X	X	X	X	X	X	X	X	X	X	X		
Physical Examination	X	X	X	X	X	X	X	X	X	X	X	X		

Protocol date: November 17, 2014

Confidential

Trial Period:	Screening Phase	Treatment Cycles									End of Treatment	Post-Treatment		
							Repeat every 12 weeks					Safety Follow-up ¹⁶	Follow Up Visits ¹⁷	Survival Follow-Up ¹⁸
Treatment Cycle/Title:	Screening Visit	1	2	3	4	5	6	7	8	9	Discontinuation			
Optional Eye Exam ¹⁹	X					X					X			
Vital Signs and Weight ⁵	X	X	X	X	X	X	X	X	X	X	X	X	X	
ECOG Performance Status	X	X	X	X	X	X	X	X	X	X	X	X	X	
12-Lead EKG	X													
Pembrolizumab Administration (30 Minute Infusion)		X	X	X	X	X	X	X	X					
Laboratory Procedures/Assessments: analysis performed by LOCAL laboratory														
Pregnancy Test – Urine or Serum β-HCG ⁸	X													
Hepatitis B/C Screening ⁷	X													
PT/INR and aPTT ⁹	X										X			
CBC with Differential ¹⁰	X ¹⁰		X	X	X	X	X	X	X	X	X	X	X	
Comprehensive Serum Chemistry Panel	X ¹⁰		X	X	X	X	X	X	X	X	X	X	X	
T3, FT4 and TSH	X ¹¹		X	X	X	X		X		X	X		X	
Efficacy Measurements														
Tumor Imaging ¹²	X					X		X ¹⁵		X			X	

Protocol date: November 17, 2014

Confidential

Trial Period:	Screening Phase	Treatment Cycles									End of Treatment	Post-Treatment		
		1	2	3	4	5	Repeat every 12 weeks					Safety Follow-up ¹⁶	Follow Up Visits ¹⁷	Survival Follow-Up ¹⁸
Treatment Cycle/Title:	Screening Visit	1	2	3	4	5	6	7	8	9	Discontinuation			
Tumor Biopsies/Archival Tissue Collection/Correlative Studies Blood														
Archival or Newly Obtained Tissue Collection ¹³	X		X								X			
Correlative Studies Blood Collection ¹⁴	X		X								X			

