13 A newly obtained biopsy sample of at least one tumor lesion or acceptable archival tissue prior to therapy start is required in all patients for PD-L1 evaluation. PD-L1 status must be assessed, and if the tumor biopsy submitted is inadequate for determination of PD-L1 status by immunohistochemistry at a central pathology laboratory, a repeat biopsy is encouraged. If a biopsy at baseline is not judged to be safe by the investigator, this requirement will be waived. Additional biopsy samples approximately at Week 3 and at disease progression are highly desirable when it is feasible. The tissue sample should have proper size to enable multiple planned biomarker analyses, and fine needle aspiration will not be acceptable. The biopsy techniques allowed in the study include core needle biopsies or surgical biopsies. Study sites should use the same biopsy techniques in this study as they routinely use for a given tumor lesion/location. Detailed instructions for tissue collection, processing and shipment are provided in section 8.2.1.														
14 Informed consent for future biomedical research samples must be obtained before the DNA sample. DNA sample for analysis should be obtained predose, on Day 1 (or with the next scheduled blood draw), as the last sample drawn, on randomized subjects only, or at a later date as soon as the informed consent is obtained. 20mL in two 10mL sodium heparin tubes will be collected at each time point.														
15 Tumor imaging should be performed at week 18 and week 24 but should be repeated only every 12 weeks thereafter or as clinically indicated.														
16 PLEASE NOTE- This visit is to be completed within 3 weeks of a patient experiencing disease progression, intolerable toxicity or withdrawal of consent. For Imaging Only- If a scan has been performed within 6 weeks of this visit, the site does not need to repeat the scan.														
17 If subjects discontinue therapy for reasons other than disease progression, they should be followed in the clinic every 3 months with surveillance studies as indicated until completion of the study. At the time of subsequent progression, if Second Cycle Treatment is not pursued, then subjects should be followed by phone contact every 3 months														
18 If subjects discontinue therapy for disease progression, they should be followed by for overall survival by phone contact every 3 months until completion of the study														

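### Serious adverse events and events of clinical interest are reportable to day 90 after treatment, but no adverse event review is scheduled after the Safety Follow-up visit, so late immune events may be under-ascertained.

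*Combined protocol and SAP*

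**What the plan says.** **Reporting windows.** ECIs, serious or not, are reportable if they are among "ECIs that occur in any subject from the date of first dose through 90 days following cessation of treatment"; the sentence goes on to close the window early if new anticancer therapy starts (Section 7.2.3.2). SAEs are reportable "from the time the consent is signed through 90 days following cessation of treatment, or the initiation of new anti-cancer therapy, whichever is earlier" (Section 7.2.3.1). Sections 5.8 and 7.1.6.3 repeat the 90 days for SAEs. For adverse events in general, Section 7.2 says "All adverse events will be recorded from the time the consent form is signed through 30 days following cessation of treatment".

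**Scheduled review.** The flow-chart row "Review Adverse Events" (Section 6.1) carries eleven marks: Cycles 1 to 9, End of Treatment and Safety Follow-up. It is blank under Follow Up Visits and Survival Follow-Up.

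**Contacts after the Safety Follow-up visit.** Patients who stop for a reason other than progression are imaged every 84 ± 7 days (Section 7.1.6.4). The flow chart also marks vital signs, ECOG status, blood count, chemistry and thyroid tests at these visits, and footnote 17 places them in the clinic. After confirmed progression or new therapy, the patient "should be contacted by telephone every 12 weeks to assess for survival status" (Section 7.1.6.4.1).

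**Timing of the Safety Follow-up visit.** The flow-chart heading and Section 7.1.6.3 put it at about 30 days. Footnote 16, attached to the same column, says "This visit is to be completed within 3 weeks of a patient experiencing disease progression, intolerable toxicity or withdrawal of consent". Section 7.1.6.3 adds: "All AEs that occur prior to the Safety Follow-Up Visit should be recorded".

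**The concern.** The plan obliges sites to report for 90 days but schedules no contact at which anyone asks about events in the last two thirds of that period. Section 5.6.1.1 explains why this period matters for this drug class: "An irAE can occur shortly after the first dose or several months after the last dose of treatment". Active questioning for ECIs is specified before each dose (Section 7.2.3.2), so it ends when dosing ends. After the Safety Follow-up visit, a new event reaches the database only if the patient or an outside physician volunteers it, or if an unscheduled visit takes place.

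Safety is a secondary objective (Section 3.2), and its analysis is a descriptive percentage of treated patients (Section 9.2.3). With at most 29 patients, one missed patient changes a reported percentage by 1/29, about 3.4 percentage points. Section 9.2.3 states no time window, so a reader of the results could not tell that days 31 to 90 had been collected differently from the period before.

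**Working it through.** The plan gives no figure of its own on this point, so the check is a comparison of dates. Days are counted from the last dose, taking cessation of treatment to mean the last dose.

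**1. Period without a scheduled query**
- End of SAE/ECI window: day 90 (Sections 7.2.3.1 and 7.2.3.2).
- Last scheduled adverse event review: day 30 (Section 6.1; Section 7.1.6.3).
- Gap: 90 − 30 = 60 days; 60/90 = 67% of the window.
- This is a maximum. If new therapy starts on day *d* between 30 and 90, the gap is *d* − 30 days; for example, *d* = 45 gives 15 days. If new therapy starts by day 30, the safety visit must precede it (Section 7.1.1.5.3) and no gap remains.

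**2. What the next contact covers**
- Patients without progression: 84 − 7 = day 77 to 84 + 7 = day 91. The visit includes laboratory tests that could reveal a hepatic or thyroid ECI, but carries no adverse event mark.
- Progressors: a survival call, with no examination or laboratory test marked.
- If an SAE/ECI question were added at this visit, the days still unqueried would be 90 − 84 = 6 at the nominal date, 90 − 77 = 13 at the earliest date, and none at day 91. These days lie inside the 60, not in addition to them.

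**3. Does other text fill the gap?**
- Section 7.1.2.1 speaks of recording during follow-up, but ties assessment to the flow chart and to clinical need.
- Section 7.1.6 likewise refers to the flow chart and adds only unscheduled visits.
- Section 7.1.6.3 follows events above Grade 1 that are already known.
- None of these schedules a question about new events after the Safety Follow-up visit.

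**4. Footnote 16 against the 30-day visit**
- If progression or toxicity is identified on the day of the last dose, the footnote requires the visit by day 21. That is 30 − 21 = 9 days before the 30-day recording period ends, and leaves 90 − 21 = 69 days (77%) without review.
- If progression is seen on the next scheduled infusion day and that dose is not given, the last dose was 21 days earlier. A day-30 visit is then 9 days after progression, and the footnote allows it as late as day 21 + 21 = 42. Here the two rules agree.
- So the rules conflict in some cases and not in others.

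**5. Illustration of scale (rates assumed; the documents give none)**
For 29 patients and a probability *p* of at least one SAE or ECI with onset between day 30 and day 90, the expected number of affected patients is 29*p* and the chance of at least one is 1 − (1 − *p*)^29:

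| Assumed *p* | Expected patients | Chance of at least one |
|---|---|---|
| 1% | 0.29 | 25% |
| 3% | 0.87 | 59% |
| 5% | 1.45 | 77% |
| 10% | 2.9 | 95% |

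These are events that would occur, not events that would be missed.

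**The case against.** The strongest reply is that the reporting duty already covers day 90 and does not depend on a mark in a chart. Sections 7.1.2.1 and 7.1.6 provide for recording in follow-up and at unscheduled visits, drug-related SAEs are reportable at any time (Section 7.2.3.1), and patients who stop without progression are seen in clinic with the laboratory tests on which two named ECI groups rest. New therapy, likely in many progressors, closes the window early. The ECI guidance appendix listed in the contents is blacked out in the public copy and may contain post-treatment instructions.

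Much of this stands, and it rules out several stronger readings:
- A reader might infer that every later contact is limited to survival or disease status. The flow chart contradicts this for Follow Up Visits; only the survival call is so limited.
- A reader might infer that events will be under-counted. Mandatory reporting remains in force and no event rate is given, so only possible under-ascertainment is supported.
- A reader might take footnote 16 as closing adverse event recording at day 21. It counts from progression, toxicity or withdrawal rather than last dose, and Section 7.2 independently requires 30 days.
- A reader might see lost events between consent and Cycle 1, because screening has no adverse event mark. The Cycle 1 review can cover that interval, and Section 7.2 already requires recording from consent.

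What the reply does not supply is a scheduled question after the Safety Follow-up visit. A duty to report what one learns is weaker than a duty to ask.

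**Conclusion.** The mismatch is real. Up to 60 of the 90 days in the SAE/ECI window have no scheduled query, and the patients most affected are progressors who have not started new therapy. The consequence is possible under-ascertainment of late SAEs and ECIs in the descriptive safety summary. Its extent cannot be estimated from the documents, and the primary response analysis is unaffected.

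The conclusion assumes that the Safety Follow-up visit takes place near day 30, that the flow-chart row is marked under the columns listed above, and that the redacted guidance adds no scheduled post-treatment query. If it does, the remaining step is to bring that query into Section 6.1. Footnote 16 is a separate inconsistency that calls for reconciliation; it does not show that data would be lost.

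**What to change.** 1. In Section 6.1, add an SAE/ECI review mark to the first Follow Up Visit and the first Survival Follow-Up call. The question should cover all events since the last contact, up to day 90 or the start of new therapy.
2. Where that contact falls before day 90, complete it with a brief SAE/ECI telephone query at or just after day 90. The 84 ± 7-day imaging schedule stays as it is.
3. Reconcile footnote 16 with the roughly 30-day timing in the flow-chart heading and Section 7.1.6.3, and align the recording cut-off in Section 7.1.6.3 with the 30 days in Section 7.2.
4. As a minor clarification only, show in the flow chart that adverse events are recorded from consent.

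The cost is one added question at a contact that already takes place, one short call for some patients, and edits to the flow chart and text. No clinic visit or scan is added.
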